3.0 SUBJECT SELECTION, RECRUITMENT, AND ENROLLMENT 3.0.1 SUBJECT SELECTION

Given the aims of this study, this protocol includes 4 populations of participants (1) youth involved in juvenile drug court, (2) caregivers of youth involved in juvenile drug court, (3) counselors providing substance abuse treatment services to youth involved in juvenile drug court, and (4) juvenile drug court personnel. The targeted enrollment is 180 youth and their families (the total number of caregivers for each youth enrolled could be greater than or equal to 1). We estimate that 374 youth and caregivers will complete the study. We will enroll up to 24 pilot cases (24 youth-caregiver pairs) for therapists training. The targeted enrollment for counselors is 8. The targeted enrollment for juvenile drug court personnel is 15. This study population will include children and may include pregnant women and prisoners. To follow is justification for including these vulnerable populations, specific benefit to their inclusion, and additional protections.

Justification for the participation of children as research subjects. The importance of the knowledge to be gained from this study lies in its compatibility with our national efforts to address the problems of adolescent substance use and maximize the benefits of juvenile drug court. The focus of this study is on whether providing incentives to caregivers participating in their adolescent's drug treatment and drug court proceedings is related to improved drug court outcomes among youth. This study is significant in that information about whether incentives may be used to effectively engage caregivers will be used for larger scale dissemination efforts.

Specific benefit to including children. There are anticipated benefits to children assigned to the intervention procedure and to children assigned to treatment as usual. The potential benefit of the

Version: 2017 09 06 Page 7 of 45

intervention is that caregivers may engage in their youth's drug treatment and drug court proceedings, leading to improved behavioral and emotional outcomes among youth in the caregiver contingency management group. Caregivers and youth may experience greater closeness and/or family involvement because of the nature of the contingency intervention. Among youth in the control group, responding to questionnaires that monitor mood and behaviors may lead to spontaneous changes due to self-reflection.

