Once a month (for 4 months), caregivers and youth in both groups will be asked to complete survey's online through RedCap. If the program is not working, caregivers and youth will complete study assessments using paper forms (or offered the opportunity to complete by phone with a research assistant). During these assessments, families will complete measures of therapeutic alliance (Working Alliance Inventory) and questionnaires that assess substance abuse and mental health symptoms in youth (Brief Problem Checklist; except in Month 3 for caregivers). Caregivers will also complete measures

Version: 2017 09 06 Page 14 of 45

assessing perception of quality/quantity of assigned homework (Homework Rating Scale). Youth will also either provide a sample for drug screen testing or the most recent results will be obtained by juvenile probation. Additional assessments will be given to the caregivers in-person to assess adolescent's substance use and mental health symptoms (Child Behavior Checklist, Month 3 only;) since the last visit; and youth will be given the Global Appraisal of Individual Needs and the Self-Report Delinquency Scale as additional measures at Month 3 only. In months 1 and 3 only, caregivers will complete the Barriers to Treatment Participation; and in month 3 (or month 4 if family is still enrolled in drug court during month 3) caregivers will also complete Barriers to Drug Court Participation. In month 4 only, caregivers will complete the Choice Questionnaire.

Study therapists will complete the Working Alliance Inventory, rating the caregiver and the youth and the Homework rating scale. During this time, Therapists in the CCM and TAU groups will also complete the Session Tracking sheets on a weekly basis.

Research assistants will rate caregiver participation weekly during months 1-4.

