7.0 STATISTICAL ANALYSIS

The research and measurement design leads to a two level data structure with repeated measurements of youth and caregiver outcomes (level-1) nested within youth/caregiver (level-2). Accordingly, the data will be analyzed using mixed-effects regression models (MRMs). This highly flexible approach accommodates several features of the proposed outcomes, including variability in the number and spacing of measurements within and between participants, a variety of outcome distributions, and potential for linear, non-linear, and discontinuous patterns of change over time.

Version: 2017 09 06 Page 19 of 45

Individual trajectories. Prior to modeling, the observed trajectory of each youth/caregiver on each outcome will be plotted using "spaghetti plots." This will illustrate sample variability in trajectories over time, within and between youth/caregiver, and will inform subsequent model specification.

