Model building & estimation. The data will be analyzed using MRMs. This approach provides a variety of options for modeling change over time, including linear, non-linear, and phase-specific (e.g., during-treatment, post-treatment) patterns of change. Prior to analysis, each outcome will be graphically and descriptively evaluated to determine the best distribution for modeling. The model building approach detailed by Singer and Willett will be used to specify fixed and random effects. First, a fully unconditional model will be estimated to determine the proportion of within- and between-subject outcome variance. Second, at the repeated measurements level, and informed by the spaghetti plots, growth terms (e.g., linear, quadratic) will be specified to explain the within-subject variance. These terms will be computed using participants' actual assessment dates, tailoring the model to the observed spacing of measurements. 100 Third, the effect of CCM will be modeled by an uncentered, dichotomous indicator (i.e., CCM = 1, TAU = 0) at youth/caregiver level (i.e., level-2), and cross-level interaction effects will be specified between the CCM indicator and the level-1 growth term(s). Before estimating the final model, fixed effect indicators will be included to test for systematic differences across therapists, providers, and districts/judges, and if identified, differences will be statistically controlled in the final model. The analyses will use an intention-to-treat approach, with youth/caregivers retained in the research measurement portion of the study independently of participation in the intervention. The models will be performed using HLM software. 101 Significance tests for variance components will be based on the likelihood ratio test, tests for fixed effects will be based on the Wald test (i.e., B / SE), and 95% CIs will be computed to reflect the magnitude and precision of the effects.

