Aim 2: Examine whether youth whose caregivers receive prize incentives (CCM) have greater reductions in drug use and criminal re-offending relative to youth receiving treatment as usual (TAU). Aim 2 will be evaluated using a series of two-level MRMs with repeated measurements of drug use and antisocial behavior (level-1) nested within youth (level-2). For urine drug screens (UDSs), the number and spacing of measurements will vary both within and across youth. For the GAIN subscales and SRD, there will be six measurements per youth, scheduled to occur at 0, 3, 6, 9, 12, and 18 months following baseline. The archival criminal charge data, which will be comprised of charge dates within youth, will be evaluated to determine the most appropriate modeling approach. For instance, if charges occur infrequently, the outcome could be the total count of charges during the 18 month period, evaluated using a single-level generalized linear model with a negative binomial outcome distribution. Alternatively, if charges occur more frequently, the outcome could be specified as the count, or any occurrence, during time periods that correspond to the research measurements. The models for Aim 2 will test for differences between CCM and TAU on the drug use and antisocial behavior outcomes at baseline and in the rate (and/or acceleration) of change over time.

Aim 3: Examine whether caregiver attendance and participation explain condition-related changes in youth drug use and criminal offending. Aim 3 will be tested using the product of coefficients

Version: 2017 09 06 Page 20 of 45

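### Therapist, provider and judge differences are controlled only if a pre-test finds them, in models with no therapist term; the harm to the CCM test depends on a therapist-by-arm layout that the plan does not state.

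*Combined protocol and SAP*

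**What the plan says.** Section 7.0 opens with "The research and measurement design leads to a two level data structure": occasions within youth/caregiver. The Aim 2 paragraph repeats the two-level form. Neither has a therapist level or a therapist random effect.

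Under Model building & estimation, as a step taken ahead of the final fit, the plan says that "fixed effect indicators will be included to test for systematic differences across therapists, providers, and districts/judges, and if identified, differences will be statistically controlled". No threshold is given for identifying a difference. The text does not say how the control is applied; keeping the indicators in the model is the natural reading. CCM enters as a 0/1 indicator at family level, alone and interacted with the growth terms. Fixed effects are tested by the ratio of estimate to standard error.

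Section 3.0.1 says "The targeted enrollment for counselors is 8", against 180 families. Families are randomized, not therapists. Section 3.0.4 describes urn randomization without naming its balancing factors, so balance by therapist is not stated. Section 5.0 (Intervention specifications) lists three providers: two use CYT with parent groups and one uses home-based MDFT.

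**The concern.** Therapists are close to the outcomes in this trial. They agree and verify the weekly targets, run the prize draws and record caregiver attendance at treatment. The plan expects their delivery to vary, because it rates CM competence and retrains low scorers. Families of one therapist may therefore resemble each other.

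A pre-test handles this poorly in two ways. A non-significant result does not show that clustering is absent, so the final model may omit a real therapist effect. A significant result brings in therapist indicators, and if each therapist works in one arm only, these carry the same information as the CCM indicator. At stake are the type I error of the CCM comparison and, in the nested case, whether it can be estimated at all. A final model that depends on a test with no stated criterion is also not fully prespecified.

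**Working it through.** The plan gives no ICC, effect size or power calculation, so it has no figure of its own to reproduce.

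**Inputs.** From the documents: 180 families, 8 counselors (a target), Wald tests with 95% intervals. Assumed: 90 families per arm, equal caseloads, ICC 0.02 and 0.05 (0.01 and 0.10 in some checks), two-sided 5% tests throughout.

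**1. Nested in arm, therapist term omitted, average-level outcome.** Design effect DE = 1 + (m - 1) x ICC; actual type I error = 2 x (1 - Phi(1.96/sqrt(DE))).

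Two caseloads fit nesting. If the 8 therapists cover both arms, m = 180/8 = 22.5. If all 8 treat CCM families only, m = 90/8 = 11.25, with TAU caseloads assumed similar.

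| m | ICC | DE | Type I error | Effective N (180/DE) |
|---|---|---|---|---|
| 11.25 | 0.02 | 1 + 10.25 x 0.02 = 1.205 | 7.4% | 149 |
| 11.25 | 0.05 | 1 + 10.25 x 0.05 = 1.51 | 11.1% | 119 |
| 22.5 | 0.02 | 1 + 21.5 x 0.02 = 1.43 | 10.1% | 126 |
| 22.5 | 0.05 | 1 + 21.5 x 0.05 = 2.08 | 17.4% | 87 |

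Simulation with 8 nested therapists, one continuous outcome per family and no true effect (8,000 runs) gave 17.7% at ICC 0.05, against 17.4% by formula. At ICC 0.10 the formula gives 27.0%.

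**2. Does the pre-test protect?** In the same simulation, an F test at 5% flagged the therapist effect in 11%, 44% and 72% of trials at ICC 0.01, 0.05 and 0.10. When it did not flag at ICC 0.05, type I error was 18.1%.

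**3. Nested, indicators retained.** Intercept + CCM + 7 therapist indicators = 9 columns, but the rank is 8. The CCM effect is not estimable; if software drops a column, it becomes a contrast between reference therapists. This needs no ICC assumption.

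**4. Contrasts of change over time.** A constant therapist shift cancels from a family's slope in a linear model. With 8 nested therapists, 180 families, six visits at 0, 3, 6, 9, 12 and 18 months and therapist variance in the intercept only, comparing family slopes gave a type I error of 4.7%. Inflation needs therapist variance in the slopes.

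**5. Crossed with arm.** The same 9 columns have rank 9. With a uniform CCM effect, type I error was about 4-5% with or without the indicators. With therapist-by-arm variance of 0.05 to 0.10 (total variance about 1, so the CCM effect varies by sqrt(0.05) = 0.22 to sqrt(0.10) = 0.32 SD between therapists), it was about 9-12% after the pre-test. Indicators for therapist main effects do not address this variation.

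**6. What a correct analysis costs.** With 90 per arm and 80% power, the detectable effect without clustering is (1.96 + 0.84) x sqrt(2/90) = 0.42 SD. For 8 nested therapists at ICC 0.05 it is 0.42 x sqrt(2.08) = 0.60 SD, or 0.72 SD using t with 6 degrees of freedom.

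**The case against.** The strongest reply is that the documents lean towards crossing. Section 5.0 mentions therapists of youth in both groups completing the termination questionnaire, and the training text has therapists delivering the conditions, in the plural, to pilot cases. With crossing and a uniform CCM effect, neither harm occurs. This carries weight, but it does not settle the layout: "Therapists in the CCM and TAU groups will also complete the Session Tracking sheets on a weekly basis" can be read either way, Section 3.0.2 says only that protocol therapists deliver CCM, and the intervention text speaks of a CCM therapist.

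Second, the planned contrasts are mainly CCM-by-time, where a constant therapist effect cancels. That stands. The design-effect figures apply to average-level comparisons, such as the Aim 1 fallback or a total charge count in Aim 2. It also means that a therapist random intercept alone would be an incomplete remedy.

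Third, with crossing, therapist indicators are estimable and defensible with only 8 therapists, where random-effect variances are poorly estimated. That stands too.

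Fourth, if provider strongly predicts attendance, the pre-test would probably keep it, and omitting a weak predictor from a family-randomized comparison costs little. This is fair. The case for always including provider is prespecification, not a likely loss.

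A reader might infer that the CCM test has a 17% type I error, or that controlling for therapists necessarily absorbs the CCM effect. The documents support neither: both need nesting, and the first also needs caseloads near 22, an ICC of 0.05 and an average-level outcome.

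**Conclusion.** The concern holds as an open risk, not a demonstrated error. The final model depends on a pre-test with no stated criterion and, with about 8 therapists, limited power. The rule is harmless if every therapist treats both arms with a uniform CCM effect, and the documents do not establish that.

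Otherwise the size depends on the layout. Nested with the term omitted gives about 7-10% type I error at ICC 0.02 and 11-17% at 0.05 for average-level outcomes; for change over time there is inflation only if therapists differ in rates of change. Nested with indicators kept leaves no estimable CCM effect. Crossed with a varying CCM effect gives about 9-12%.

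The ICCs and the therapist-by-arm variances are assumptions. The percentages are for a continuous outcome with equal caseloads and will differ for the Bernoulli and growth models. The rank result does not depend on these assumptions.

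**What to change.** Amend Section 7.0 as follows:

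- State whether therapists are crossed with arm or nested in it.
- Drop the test-then-control rule. Always include provider as a fixed effect, and decide in advance whether a district/judge term enters.
- Prespecify a therapist random intercept. For change-over-time contrasts, add a therapist random effect on the growth term. If therapists are crossed with arm, add a therapist-by-CCM random term.
- Use small-sample degrees of freedom for the CCM contrasts where the outcome model allows, in place of the plain Wald ratio.
- Do not use therapist fixed indicators if therapists are nested in arm. If they are crossed, prespecified indicators are an acceptable alternative to the random intercept.

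This is mainly SAP wording. Therapists complete session tracking sheets in both groups, so each family's therapist should be identifiable. The downside is somewhat wider intervals and imprecise variance estimates with about 8 therapists.

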2.0 STUDY OBJECTIVES

Version: 2017 09 06 Page 6 of 45

The previous section highlighted the need for practical, easy-to-implement ways of improving caregiver participation in JDC and youth drug treatment. An extensive literature provides strong evidence that CM is efficacious with both youth and adults in promoting drug abstinence, ^{10,11} treatment attendance ^{12,13} and participation, ¹⁴ and completion of treatment related activities such as medication compliance ¹⁵ and competing behaviors that are incompatible with drug use (e.g., family activities, employment ¹⁶). The purpose of the proposed study is to evaluate the effects and acceptability of Prize CM procedure ¹⁷ designed to reinforce caregivers' engagement in JDC and their child's drug treatment (Caregiver CM; CCM). If successful, this study will provide important information that can be used to reduce youth offending and drug use, and importantly, inform clinical care practices in the emerging field of JDCs. **Specific aims of this study include**:

- **Aim 1:** Evaluate whether caregivers receiving prize incentives (CCM) for attendance and participation in JDC and adolescent drug treatment show greater attendance and participation in JDC and adolescent drug treatment relative to caregivers not receiving CCM (i.e., JDC TAU). *Hypothesis 1*: We predict that caregivers who receive CCM will have higher rates of attendance/participation in JDC and in therapy than will TAU caregivers.
- **Aim 2:** Examine whether youth whose caregivers receive prize incentives (CCM) have greater reductions in drug use and criminal re-offending relative to youth receiving TAU. Hypothesis 2: We predict that youth in the CCM condition will experience greater reductions in drug use and less re-offending.
- **Aim 3:** Examine whether caregiver attendance and participation explain condition-related changes in youth drug use and criminal offending.
- Hypothesis 3: We predict that caregiver engagement in drug court processes and adolescent drug treatment activities will be associated with stronger reductions in adolescent drug use and other problem behavior, which do not specifically focus on caregiver engagement.

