Caregiver Participation Measures. Multiple measures and multiple informants will be used to assess caregiver participation in JDC weekly status hearings and treatment sessions. Caregiver attendance in JDC will be independently recorded by the JDC supervisors or research assistant using the Parent/Caregiver Drug Court Attendance Form and collected weekly at drug court. Differences between research assistants and supervisor reports will be reconciled using court records. Drug court records will also be reviewed for caregiver and youth attendance and unexcused absences at drug court sessions. Quality of caregiver participation in drug court will be recorded using the Juvenile Drug Court Caregiver Participation Ratings form, which will be completed by a research assistant. Barriers to Drug Court participation will be measured using the Barriers to Drug Court Participation measure, which will be completed by the caregiver. Similarly, caregiver attendance at youth treatment sessions will be recorded by therapists and measured as a percent of scheduled sessions using the Caregiver Contingency Management Session Tracking Sheet (CM Group) or Caregiver Treatment as Usual Session Tracking Sheet (Treatment as Usual Group); Barriers to Treatment participation will be measured using the Barriers to Treatment Participation measure, which will be completed by the caregiver. See the schedule of assessments table below for timing of assessment.

Implementation fidelity. The 12-item Contingency Management Competence Scale (CMCS) assesses fidelity to prize-based CM procedures. The CMCS has good inter-rater reliability, internal consistency, discriminant, concurrent and predictive validity in substance abusing outpatients. In the present study, the CMCS will be used to rate CCM audiotapes. Initially, 100% of audiotapes will be reviewed to establish inter-rater reliability. Subsequently, the CMCS will be used to assess treatment fidelity. Treatment implementation will also be measured using the Caregiver Contingency Management tracking sheet, which will be completed by the therapist. The Caregiver Contingency Management tracking sheet will track number of prize draws provided to families at each session and the associated activities. To maintain balance across the treatment groups, a comparable measure will be given to the treatment as usual group, Caregiver Treatment as Usual session tracking sheet.

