agreed upon by the CCM therapist and the caregiver a priori each week. It is expected that these activities will vary from week to week and from family to family. For example, adolescents will not have court dates every week and clinicians occasionally cancel substance abuse treatment sessions (making it impossible for the family to attend). Thus, we plan some flexibility around reinforced activities while also requiring that the activities reinforced must be related to drug court outcomes. Importantly, regardless of the activities planned, the therapist and caregiver must establish an a priori way to verify that the activity was completed. The verification will be required for the caregiver to receive reinforcement. The specific activities reinforced will be documented and tracked each week by the CCM therapist in collaboration with the caregiver. Caregivers will be allowed escalating numbers of draws from a prize-urn for completing the pre-arranged and verified target activities. The CCM prize-urn will be implemented by the therapist once per week. Following the initial session with the CCM therapist, the caregiver will receive one draw from a prize-urn for each successfully completed activity (up to three). For each subsequent session in which the caregiver completes the target activities, the number of draws will increase by one, and keep increasing weekly up to a maximum of five draws per behavior on any one occasion. Thus, it would be possible for caregivers to reach a maximum of 15 draws per week. If the caregiver does not meet an agreed upon target (e.g., does not attend JDC, drug treatment, or does not complete homework assignments), he/she will not receive a prize draw and the number of draws will be reset to one for each target behavior at the next session. Thus, although caregivers may receive reinforcement for one or two completed behaviors (out of a possible three), failure to complete three assigned behaviors will result in a reset of prize draws for the next session. The only exception to this rule will be if the caregiver: 1) experiences an event that is out of his/her control that prevented completion of the target behavior (e.g., documented family emergency or cancelled court date); and 2) he/she was unable to reach the CCM therapist to arrange for another activity. "Excused misses" will not result in a reset of prize draws. The prize-urn in the present study is similar to the one used in two recent studies of adults in substance abuse treatment. It will be filled with 500 slips of paper, with 50% (250) not resulting in a prize ("good job"), 175 (35.0%) small prizes (worth about \$1), 74 (14.8%) large prizes (worth \$20), and one (.2%) jumbo prize (worth \$100). Thus, the average value of each prize draw is \$3.51, and a caregiver who participates for 16 weeks can earn up to a maximum average of \$737.10 in prizes.

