Aim 1: Evaluate whether caregivers receiving prize incentives (CCM) for attendance and participation in JDC and adolescent drug treatment show greater attendance and participation in JDC and adolescent drug treatment relative to parents not receiving CCM (i.e., JDC TAU). The data for evaluating this aim have a unique structure – caregivers will have different numbers of opportunities for attendance and participation. MRMs, however, readily accommodate this feature. The data will be structured with multiple scheduled dates for each youth/caregiver, and for each date, a value of 0 or 1 will reflect the attendance and participation status. The dichotomous attendance and participation outcomes will be modeled using a Bernoulli outcome distribution with a logit link function and Laplace approximation of the maximum likelihood function. The formulation will compare CCM and TAU on their change over time in attendance and participation. Of note, if the model building steps reveal low within-caregiver variability in attendance and participation, an unconditional level-1 model will compare CCM and TAU on the overall average level of attendance and participation.

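### Hypothesis 1 predicts higher attendance, but the comparison named for Aim 1 is change over time, which is zero when the benefit is immediate and constant

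*Combined protocol and SAP*

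**What the plan says.** Three places define the Aim 1 question as one of level.

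- Section 2.0, Hypothesis 1: "We predict that caregivers who receive CCM will have higher rates of attendance/participation in JDC and in therapy than will TAU caregivers".
- Section 7.0, the Aim 1 statement, which asks whether attendance and participation are greater under CCM.
- Section 4.0, Caregiver Participation Measures, where attendance at treatment sessions is "measured as a percent of scheduled sessions".

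The Aim 1 analysis paragraph in Section 7.0 codes each scheduled date as 0 or 1, fits a Bernoulli mixed model with a logit link, and then says: "The formulation will compare CCM and TAU on their change over time in attendance and participation". Level enters only by exception: "if the model building steps reveal low within-caregiver variability in attendance and participation, an unconditional level-1 model will compare CCM and TAU" on their overall average. No cut-off for low variability is given.

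The general text under Model building & estimation adds three relevant points. Its first step is that "a fully unconditional model will be estimated to determine the proportion of within- and between-subject outcome variance". Later, "the effect of CCM will be modeled by an uncentered, dichotomous indicator", together with interactions between that indicator and the growth terms. Fixed effects get Wald tests and 95% confidence intervals. The text also allows "linear, non-linear, and phase-specific (e.g., during-treatment, post-treatment) patterns of change".

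For Aim 2, by contrast, the plan names both the baseline difference and the rate of change as things to be tested.

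**The concern.** A comparison of change suits an outcome measured before treatment starts. Aim 2 has such a measurement. For attendance no pre-randomization window is specified, and the incentive acts almost at once (Section 5.0, Caregiver Contingency Management): "Following the initial session with the CCM therapist, the caregiver will receive one draw from a prize-urn" for each completed activity. The arms can therefore already differ at the first analysed dates. If the gap then stays the same, there is no difference in change to find. If it narrows, the difference in change is negative, which describes fading and not harm.

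The risk is a null or apparently adverse Aim 1 result for an intervention that raises attendance as hypothesised. The CCM main effect in the same model could rescue the conclusion. However, the plan does not say which coefficient decides Aim 1 or at which time point the main effect is read, so that choice could be made after the data are seen.

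**Working it through.** The documents give no power calculation or effect size for Aim 1, so there is no stated figure to reproduce.

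**Algebra.** With linear time, scaled as weeks from entry divided by 16, the planned model is

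logit p = b0 + b1·t + b2·CCM + b3·CCM·t (plus a caregiver random effect).

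The named comparison is b3. The main effect b2 is the gap at t = 0. The average gap over the period is b2 + b3·t̄, with t̄ about ½. For an average log-odds gap δ:

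- constant benefit: b2 = δ, b3 = 0, average δ;
- benefit rising from zero: b2 = 0, b3 = 2δ, average 0 + 2δ·½ = δ;
- benefit fading to zero: b2 = 2δ, b3 = −2δ, average 2δ − 2δ·½ = δ.

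The same average benefit therefore gives a zero, positive or negative b3. Only the average contrast is unaffected by the shape.

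**Simulation inputs.**

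- TAU attendance 40%: cited in Section 1.0 from one non-randomized drug court study.
- CCM 55%: assumed.
- Random-intercept SD 1.0, 1.3 and 1.5 on the logit scale: assumed.
- 16 weekly dates: assumed, matching the 16-week CCM period.
- 90 families per arm: 180 from Section 4.0, with equal allocation assumed.

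If 40% and 55% describe the median caregiver, δ = ln(0.55/0.45) − ln(0.40/0.60) = 0.201 + 0.405 = 0.61. If they are population averages, δ rises to as much as 0.86 at SD 1.5. The ranges cover both readings and all three SDs. Models were fitted by maximum likelihood with Gauss–Hermite quadrature, 600 trials per cell, with Wald tests at two-sided 5%.

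**Share of trials significantly favouring CCM (except where marked)**

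| Pattern of benefit | CCM-by-time | CCM at time 0 | 16-week average |
|---|---|---|---|
| (a) Constant, attendance flat | 2–3% | 56–89% | 72–99% |
| (a2) Constant, both arms falling 1.0 logit in parallel | 2–3% | 56–90% | 71–99% |
| (b) Builds over 5 weeks, then constant | 21–39% | 21–38% | 57–96% |
| (c) Rises from zero over 16 weeks | 99–100% | 1–2% | 69–99% |
| (d) Fades to zero by week 16 | negative in 98–100% | 99–100% | 71–99% |

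One cell of (a) as an example, SD 1.3 with the median-caregiver reading: CCM-by-time 2.3%, time 0 63%, average 82%. Pattern (b) follows the prize schedule, in which draws per behaviour rise weekly to five. Adding a quadratic term and testing both CCM-by-time terms jointly raises (b) only to 26–47%.

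**Sensitivity.**

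- Random slopes (SD 0.5–1.0 logit per 16 weeks): (a) 1–3% for CCM-by-time against 68.5–99.5% for the average; (d) negative in 95–100%.
- Eight dates: (a) 2–3% against 66–98%; (d) negative in 81–98%, average 53–95%.
- CCM 50% or 60% in (a): CCM-by-time stays at 2–3%, average 38–86% or 93–100%.
- With no effect, both tests reject about 5% (average 4.8–5.3%).
- A separate check used a population-average logistic model with cluster-robust tests and a constant benefit. CCM-by-time was rejected, in either direction, in 4.3–6.7% of trials across 18 settings. For 40% against 60%, 16 dates and SD 1.0, it was rejected in 5.0%, against 100% for average level.

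**The switch.** If low variability means the variance share from the first step, take the latent logistic scale, where within-caregiver variance is π²/3 = 3.29. The within share is 3.29/(3.29 + 1.0²) = 77% at SD 1.0 and 3.29/(3.29 + 1.5²) = 59% at SD 1.5. Neither is plainly low, and neither shows whether the arms run in parallel. If it means that no growth term is needed, the switch covers (a). It does not cover (a2), where the pooled time trend is significant in 100% of trials.

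**The case against.** The strongest reply is that the level effect is already in the plan. The general model contains a CCM indicator with a Wald test and confidence interval, and that text calls it the effect of CCM. In (a), (a2) and (d) this term often or nearly always favours CCM, and in (c) the interaction does. Only (b) is weak on both. This stands as a description of the model, and it means the defect lies in which coefficient is named and not in what the model can estimate. It does not settle the matter. Aim 1 names the other coefficient, and the main effect ranges from 1–2% to 99–100% across patterns with the same average benefit, because it is read at a time point the plan does not state.

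Second, the switch to average level can be read as applying when attendance does not change, since it refers to the model-building steps as a whole and drops the growth terms. That reading is reasonable and would cover (a). It leaves (a2), (b) and (d) untouched, and still gives no criterion.

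Third, draws escalate, so a growing benefit is plausible, and the plan allows non-linear and phase-specific change. A benefit rising throughout the period would indeed be detected better as planned. But draws per behaviour are capped at five, so escalation can end early in a 16-week period.

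Fourth, most of the inputs are assumptions, court dates are not weekly, and the 40% refers to court attendance only. That is true of the power figures. It is not true of the chance-level result in (a) and (a2), which is algebra.

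Finally, a joint two-degree-of-freedom test of CCM and CCM-by-time would also perform well (58–100% across (a) to (d)). The plan does not name it, and by itself it does not say whether attendance is higher on average.

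**Conclusion.** The concern holds, and the text should be corrected before the data are analysed. The only comparison named without condition for Aim 1 does not test Hypothesis 1. For any benefit constant in log-odds from the first dates, it favours CCM at the chance rate of 2–3%, whatever the effect size or random-intercept SD. For a fading benefit it is significantly negative in 98–100% of trials under the stated assumptions. For a benefit that builds over five weeks it has 21–39% power, against 57–96% for the average.

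The exact zero depends on constancy on the logit scale: if TAU attendance drifts, a benefit constant in percentage points gives a non-zero interaction. The remaining power figures depend on the assumed 55%, the SDs, the number of dates and equal allocation. The data and model can answer the hypothesis; the plan has not committed to the coefficient that does so.

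**What to change.** In the Aim 1 paragraph of Section 7.0:

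1. Name as the primary contrast the CCM–TAU difference in average attendance, and likewise participation, over scheduled dates in the 16-week CCM period, from the same Bernoulli mixed model. With linear time, centring time at mid-period makes the CCM coefficient this average on the log-odds scale. With quadratic or other growth terms, specify the contrast averaged over the dates. If a difference in percentages is wanted, derive it from the fitted model.
2. State the time origin.
3. Make CCM-by-time secondary, as a description of whether the benefit grows or fades.
4. Delete the low-variability switch, which is then unnecessary.
5. State whether court dates after the CCM period are analysed. The Section 8.0 activity tables leave this open (52 attendance forms; participation ratings over 4–6 months). If they are, use the phase-specific term that Section 7.0 already allows.

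The change is to SAP wording only; data, model and software stay the same. The price is lower power if the benefit rises steadily over the whole period: 69–99% against 99–100% for the slope test, or 66–99% against 95–100% with random slopes.
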